C.5.e. Treatment as usual (TAU). The control condition in Trial 3 will consist of having the family participate in the existing clinical services offered by the therapist over the 12-week period. After 12-weeks they will be asked to sign a release of information to have the any outside treatment records sent for review by the study staff. The records will be coded for treatment components. As the post-study evaluations, patients in the TAU condition will receive Anxiety Coach and be offered additional treatment as needed.

C.6. Design Considerations

C.6.a. Justification of Experimental Design. The use of three conditions across two trials allows for an examination of the effects of *Anxiety Coach* and direct therapist contact. Specifically, the **TAU vs. FTF-AC comparison** provides an estimate of the feasibility and palatability of *Anxiety Coach* to therapists, a measure

of the extent to which the application facilitates therapists' use of exposure-based methods, the usefulness of *Anxiety Coach* for disseminating evidence-based CBT methods to community therapists, and its value for facilitating treatment adherence among patients with anxiety disorders. Randomizing therapists/patients to one of two conditions removes the potential for bias to affect recruitment, keeps the evaluators blind to experimental condition, removes concerns with order effects, and allows for the more patients to be treated simultaneously thus decreasing the length of the study. **The MC-AC vs. TAU comparison** provides an estimate of the feasibility as well as the impact on acceptability and outcome of using *Anxiety Coach* with limited direct therapist contact as a method for extending treatment outside of the brick and mortar mental health settings. To increase the real-world generalizability of the study, the study will not pay for therapy, but patients in all conditions will be reimbursed for participation in assessments and will be allowed to keep the iPod Touch.

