If therapists in Trial 1 choose to use Anxiety Coach in their practice during, those patients will not be engaged in any research activities. In order to use the application the patient must agree to the terms of use that explain what data Mayo Clinic collects and how these data are used.

C.7.e. Treatment Assignment. For Trial 2, therapists will be randomized to either TAU or FTF-AC after they are consented. The therapist will then offer participation to the next patient they see likely to qualify. (If needed, the second patient treated by a therapist randomized to TAU will be enrolled in the FTF-AC condition.) This format clearly differentiates the therapists' participation in the study from the patients' participation. To limit bias in enrollment, neither patients nor the independent evaluators will be aware of therapeutic condition at the time of enrollment. Treatment in each condition can begin within 1 to 2 weeks of the evaluation as soon as the patient has completed the study evaluation. All patients will be informed that participation in the study includes the possibility of enrollment into either of two conditions. If patients discontinue treatment prematurely, before the sixth session, they will not be replaced with another patient. Instead efforts will be made to complete early withdrawal post-treatment evaluations on all enrollees and the frequency of premature discontinuation will be compared between conditions. For Trial 1, the therapists will have access to the Anxiety Coach application and can use it as they choose in their clinical practice. For Trial 3, treatment assignment will occur following consent and the pre-evaluation is completed.

C.7.f. Therapists, Treatment Integrity and Competence. Therapists in Trials 2 and 3 will provide treatment. To determine the success of creating conditions with distinct therapist behavior, all sessions and communication in each condition will be recorded and coded for use of exposure and other interventions. In the TAU condition, the therapist will not receive any instruction regarding the content of treatment. In all three conditions across the two trials the intervention specialists or the PI will monitor and support the therapists' compliance with guidelines. The intervention specialists have highly developed therapeutic skills, at least five years' experience providing CBT to children with anxiety disorders and their families, extensive one-on-one

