C.8.c. Recruitment. The current recruitment strategy is intended to approximate the conditions under which *Anxiety Coach* would have the most impact, i.e. areas where psychiatric needs exceed mental health providers with specialization in CBT for childhood anxiety disorders. To maximize external validity the experimental treatment will be implemented by community therapists recruited from a large geographical area, particularly areas with a mental health shortage designation, and treatment will be paid for through traditional clinical mechanisms.⁷⁸ The principle limitation of the recruitment paradigm is that only patients with access to services will be included in the study. However, this study will establish the safety and efficacy of *Anxiety Coach* with differing levels of therapeutic contact before examining *Anxiety Coach* as a no contact treatment where it would be more difficult to address problems with safety, usability, or lack of progress. We anticipate that the data from the proposed study will prepare for future projects extending services to those outside the system by: a) improving the application; b) documenting the utility of *Anxiety Coach*; and c) creating a web-based portal

through which people in need of treatment could be followed by a provider with whom they have never had face-to-face contact.

C.8.d. Treatment Protocols. For Trials 2 and 3 the guidelines for each intervention instruct the therapist to interact (face-to-face or via the web-portal depending on the condition) once per week for 6 to 12 weeks. Although therapists are not given further instructions on how to deliver *TAU*, the six-session minimum will likely result in a higher level of care than is typically received in real-world settings, since standardization of contact across the interventions is necessary to examine the ability of *Anxiety Coach* to increase provider use of exposure.

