C.10.c. Attrition, Noncompliance and Missing Data. The intention to treat analysis set will serve as the principal analysis set. Attempts will be made to minimize the missing data due to missed visits (i.e., fewer than the required six appointments). To handle missing data the following approach will be used. The analyses of the primary outcome will be performed in two ways: 1) using complete case scenario i.e., those patients that

July 1, 2019 (Version 12)

have data available on both time points and 2) imputing a rank from the earlier time point carried forward. Last rank carried forward has been shown to have better statistical properties than the last observation carried forward approach. In addition to these, we will also explore other sensitivity analysis such as imputation of a mean or median or worst or best case values in the respective groups. Findings from sensitivity analysis will be viewed in light of primary analysis prior to reaching final conclusions and interpretation of the results.

PROTECTION OF HUMAN SUBJECTS

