One potential risk of participating in this project includes discomfort during the data collection (survey, phone screenings, and assessments) related to discussing sensitive topics and the length of the evaluation. However, the length of material completed by therapists are minimal and the patients in the study are seeking treatment and presumably are interested in discussing their symptoms with an expert clinician. It is estimated that the survey will require 20 to 30 minutes to complete, and the patient interview and questionnaire completion will take approximately 2-3 hours for the initial evaluation and 1-2 hours for the post-treatment assessment. Having the family complete questionnaire packets at home where the family can work at their own pace and take breaks will minimize the burden associated with lengthy assessments.

Although difficult to predict with certainty, the degree of risk and benefit may differ among the three conditions. Neither the relative benefit of augmenting face-to-face therapy with *Mayo Clinic Anxiety Coach* nor the relative risk of minimal contact treatment have yet been tested, and so the relative cost-benefit ratios are uncertain. The risk of being randomized to TAU is that the patient may receive a potentially less effective treatment. However, as this treatment is the standard intervention outside the study, participation in the study will not have a detrimental effect on the quality of the patient's treatment. In fact, the study requirement of a minimum of 6 sessions will likely result in a higher level of care. Further, there is no portion of the study during which patients will be asked to receive no treatment. Alternatively, patients in the minimal contact *Anxiety Coach* condition may be at risk of receiving a less effective treatment because of the decreased therapist contact. However, the goal of the study is to examine the feasibility of minimal contact treatment. Thus, patients may receive emergent care or more frequent contact if needed. Such occurrences will be collected as measures of tolerability. Within all conditions if additional care is clinically indicated the therapist (with the assistance of the study staff under the direction of [name]) will assist the family in making arrangements for appropriate care.

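### Contact, recording and monitoring statements take in Trial 3 usual care, which guarantees none of them, and that arm's Time 2 depends on a start date the study does not control

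*Protocol*

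**What the plan says.** **General statements.**

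- C.8.d: "For Trials 2 and 3 the guidelines for each intervention instruct the therapist to interact" once a week for 6 to 12 weeks, in person or through the portal according to condition. The paragraph refers to a six-session minimum under TAU and justifies it "since standardization of contact across the interventions is necessary to examine the ability of" Anxiety Coach to raise providers' use of exposure.
- 4.1.1.c, on the risk of being randomized to TAU: "the study requirement of a minimum of 6 sessions will likely result in a higher level of care". No trial is named.
- C.10.c, on missing data: "missed visits (i.e., fewer than the required six appointments". Again no trial is named.
- C.7.f, which opens by naming Trials 2 and 3: "all sessions and communication in each condition will be recorded and coded for use of exposure and other interventions". It continues: "In all three conditions across the two trials the intervention specialists or the PI will monitor" and support compliance with the guidelines.

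**What the Trial 3 control arm gets.** Under C.5.e the family is to "participate in the existing clinical services offered by the therapist over the 12-week period". After 12 weeks the family is asked to release outside records, which are coded for treatment components. C.3.b (Trial 3) places this care in the community or within the sponsor's institution, with someone other than the current therapist. Its data list has questionnaires and application data but no session recordings.

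**Timing.** C.7.e: "For Trial 3, treatment assignment will occur following consent and the pre-evaluation is completed". C.7.g expects treatment to begin one to two weeks after baseline and puts Time 2 at 12 weeks (+/- 2) after the first treatment session. C.10.b.2 compares symptom change between groups by repeated measures ANOVA, as an exploratory analysis meant to yield effect estimates for a later trial. The SAP presents pre- and post-treatment symptom measures by patient and condition and adds no timing rule.

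**The concern.** A reader of C.8.d, C.10.c or 4.1.1.c would conclude that a Trial 3 control child is assured at least six sessions. A reader of C.7.f would conclude that those sessions are recorded and the therapist monitored. The section that defines the arm assures none of this. Section 4.1.1.c matters most, because it offers the minimum as a protection for children assigned to TAU.

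The second issue is the assessment anchor. In the minimal-contact arm (MC-AC), study staff deliver the treatment and know when it starts. In the control arm the first session happens after randomization, with a provider outside the study's control. If that session is late, Time 2 moves later from baseline than in MC-AC. If it never happens, Time 2 has no defined date, although C.10.c makes intention-to-treat the principal set. The affected result is the MC-AC versus TAU symptom contrast.

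**Working it through.** **Step 1: set the statements against the arm definition.**

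| Element | Stated generally in | Provided for Trial 3 TAU in C.5.e |
|---|---|---|
| Weekly contact, 6 to 12 weeks | C.8.d | No |
| Minimum of six sessions | C.8.d, 4.1.1.c, C.10.c | No |
| Recording and coding of all sessions | C.7.f | No; outside records coded afterwards |
| Compliance monitoring | C.7.f | No |

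The number of contacts assured is therefore at least 6 on the general text and 0 on C.5.e. One likely source is that C.7.f counts three conditions across two trials, which merges two different TAUs: the Trial 2 version in C.5.b (6 to 12 sessions with session recording) and the Trial 3 version in C.5.e. For MC-AC the weekly rule does hold, since C.5.d requires at least weekly electronic contact for 6 to 12 weeks.

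**Step 2: Time 2 window as planned.** Let s be the week of the first session, counted from baseline. From C.7.g, s is 1 to 2 and Time 2 = s + 12 +/- 2.

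- Earliest: 1 + 12 - 2 = 11 weeks from baseline.
- Latest: 2 + 12 + 2 = 16 weeks.
- Nominal: 1 + 12 = 13 to 2 + 12 = 14 weeks.

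**Step 3: late control start.** The documents give no control start delays, so these values of s are assumptions.

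| s (weeks) | Control window, s + 10 to s + 14 | Overlap with 11 to 16 |
|---|---|---|
| 4 | 14 to 18 | Partial |
| 6 | 16 to 20 | Touches at 16 only |
| 8 | 18 to 22 | None |

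Overlap is lost when s + 10 > 16, that is, s > 6. With no first session, s does not exist and neither does the window.

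**Step 4: can the date be known in time?** C.5.e requests records only after 12 weeks and only with a signed release. It names treatment components as what is coded, not session dates or counts. No section describes learning the start date while the child is being followed.

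**Step 5: a fixed point from baseline.** The latest nominal time in step 2 is 2 + 12 = 14 weeks. With +/- 2 the window is 12 to 16, inside 11 to 16. A child starting on plan is then seen 14 - 2 = 12 to 14 - 1 = 13 weeks after the first session. At the extreme, a week-1 start seen at week 16 gives 15 weeks, one more than C.7.g now allows.

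**The case against.** **The specific sections already point to Trial 2.** C.5.a limits weekly specialist review to Trial 2. C.5.b labels its 6-to-12-session TAU as Trial 2. C.3.b lists audio recordings for Trial 2 and not for Trial 3. C.9.f pairs TAU with FTF-AC. The reason given in C.8.d for standardizing contact, providers' use of exposure, is the Trial 2 question. The manual described in C.3.a.2, which is to include TAU instructions, is not among the documents. This stands as evidence of intent, and it makes the first half of the point largely a matter of wording. It does not correct the general statements. The reassurance in 4.1.1.c still describes a protection that C.5.e does not give.

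**The start date may be recoverable.** A reader might infer that the study never captures it, or that missed appointments cannot be identified in this arm. The documents do not support that. C.5.e requests outside records, and C.3.b lists therapist, patient and parent questionnaires for Trial 3 without limiting them to one arm. What remains is that no prospective capture is specified and that the records come too late to schedule the visit.

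**Late starts are hypothetical.** C.7.e and C.7.g plan for treatment to begin within one to two weeks in each condition. C.5.e refers to a 12-week period and a post-study evaluation, and C.7.e seeks early-withdrawal evaluations on all enrollees, so a child who never starts is not simply lost. This is fair, and it is why no bias is claimed. But the planned start is an expectation about care the study does not deliver, and the 12-week period in C.5.e has no stated beginning.

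**The analysis is exploratory.** C.10.a and C.10.b.2 say so. No sample size, error rate or confirmatory test depends on this, and the severity is set accordingly.

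**Conclusion.** The point holds at minor severity. C.8.d, C.7.f, C.10.c and 4.1.1.c make statements about contact, minimum sessions, recording and monitoring that C.5.e does not support for Trial 3 TAU. The Time 2 rule in C.7.g rests on an event that the study does not control in that arm. A late start would give unequal intervals between arms, with no overlap beyond week 6, and no start would leave the interval undefined.

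The timing figures use the start and window in C.7.g; the late starts are assumptions. A reader might infer that the Trial 3 estimate is biased in some direction. The documents give no delays from which to argue that. Nor does the point imply that usual care needs a six-session floor: uncontrolled contact is a legitimate feature of a usual-care comparison. In 4.1.1.c only the six-session sentence lacks support for Trial 3 controls; the argument that TAU is the standard intervention stands. Trial 2 is unaffected.

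**What to change.** 1. **Limit the statements.** In C.8.d and C.7.f, confine weekly contact and compliance monitoring to Trial 2 and MC-AC. Confine the six-session minimum (C.8.d) and the six required appointments (C.10.c) to Trial 2, with six weekly contacts as the MC-AC equivalent. Confine recording to Trial 2 sessions and MC-AC communication. In 4.1.1.c, remove the six-session reassurance for Trial 3 controls. Impose no minimum on Trial 3 TAU.
2. **Fix Time 2 in Trial 3.** In both arms, schedule it 14 weeks (+/- 2) after the baseline evaluation, whenever or whether treatment starts. Baseline is a known date for every child. A rule triggered by a late start would need information that may arrive only at or after the visit, and a rule for controls alone would itself create a timing difference between arms.
3. **Count contacts.** From the records already requested, with one parent item at Time 2 as back-up, extract the first-session date and number of sessions. Report contacts received by arm, including none, beside the Trial 3 symptom result, described as MC-AC versus usual care with uncontrolled contact.

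**Cost.** Wording changes in four sections and a Trial 3 scheduling sentence in C.7.g, two extra record fields and one parent item. The risk-benefit text becomes slightly less favourable for Trial 3 controls. Late starters are assessed after less care: an assumed start at week 8 leaves 14 - 8 = 6 weeks by Time 2. That is part of usual care and would be visible in the contacts table. Consent pages are not available, so no consent change is claimed.

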Trial 1. In Trial 1 (Acceptability) we will gather acceptability and usability data from up to 30 therapists. After being consented therapists will complete a packet of information about how they treat child anxiety and their beliefs about treatment related issues. Each therapist will then receive training from a study intervention specialist on how to use Mayo Clinic Anxiety Coach. The therapists will be given access to use Mayo Clinic Anxiety Coach and be given an iPod Touch and can incorporate it into their practice as they desire for a period of six months during which time the therapists will have access to the intervention specialist to answer questions about how to use the application. To protect patient confidentiality, the system will generate numerical identifiers (e.g. Patient #1) and therapists will only be able to enter ages into the system, rather than full names and birthdates. Therapist will be asked to complete questionnaires about how they treat child anxiety and their beliefs about treatment related issues as well as questionnaires about usability and how they integrated Anxiety Coach into their practice two weeks and six months after completing the training. In addition, data automatically recorded through any use of the application will be analyzed.

Trial 2. In Trial 2 (Increasing Exposure Use) 30 therapists will be randomized to treat 30 children with anxiety disorders with treatment as usual or FTF-AC. (If necessary due to limited therapist availability, therapists randomized to TAU will treat a second patient with FTF-AC). Therapists and patients/parents will be consented. Data collection will include questionnaires completed by therapists, patients, and parents before and after treatment, as well as audio recordings of sessions, and data automatically saved by the application.

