supervision from [name], attendance of workshops on anxiety treatment, and been involved in the development of *Anxiety Coach*. [name] will train the intervention specialists in the procedures outlined in the UPM for supporting therapists, meet weekly for supervision, and provide additional supervision as needed for concerns about a therapist's use of the study interventions or a patient's progress, clinical deterioration, or development of new symptoms.

C.7.g. Assessment Timeline. Patient participants will receive two assessments conducted via videophone by a trained independent evaluator blind to condition under the supervision of [name]. The initial assessment will be conducted at baseline (Time 1) when the patient's eligibility is determined. The patient will begin treatment within one to two weeks. The patient's response to treatment will be assessed 12 weeks (+/- 2 weeks) after the initial treatment session (Time 2). The evaluations will be comprehensive in nature (e.g., diagnostic interview, clinician ratings, parent- and self-reports). Accommodations will be made for families without electronic access, such as videophone assessments in the therapist's office. Beginning at the baseline assessment and continuing throughout the study, patients will rate their daily symptoms with an iPod Touch. Therapists in Trial 1 will complete the survey materials from Phase I inquiring about treatment practices and beliefs prior to receiving training in the use of *Anxiety Coach*. Two weeks after receiving *Anxiety Coach* training the therapists will be asked to complete the same survey material plus measures assessing software usability. 6 months after the initial training, therapist will be asked to complete the survey material, usability measure, and a questionnaire about their actual use of *Anxiety Coach* since the training.

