C.9. Description of Assessment Measures. In Trial 1 therapists will complete study measures before training, two weeks after training, and then six months later. In Trials 2 and 3, all study measures will be completed at pre- and post-treatment assessment periods except as noted below. Independent evaluators under the supervision of [name] blind to study condition will administer clinician-rated instruments. Therapist, parent and child report will be completed online via the Survey Research Centers electronic survey tools (or by paper and pencil and return via mail if completion electronically is not available).

C.9.a. Clinician-Administered Measures: Anxiety Disorders Interview Schedule for DSM-IV-Child Version Child and Parent Interview Schedules (ADIS-IV-C/P).⁷⁹ The ADIS-IV-C/P are structured interviews to assess the child's symptoms. Diagnoses reflect endorsement of symptoms as well as a severity rating (patient impairment/distress) of at least 4 on a 0-8 scale. The ADIS-IV will be administered in its entirety to the child and the parent together at pre- and post-treatment to determine whether an anxiety disorder is the primary diagnosis and the presence of comorbid diagnoses. Pediatric Anxiety Rating Scale (PARS).⁸⁰ The PARS is a summation of six items assessing anxiety severity, frequency, distress, avoidance, and interference and has been used as the primary continuous outcome measure in treatment studies.³⁰ Clinical Global Impression-Severity and Improvement (CGI-S/I).⁸¹ The CGI-S/I is a 7-point clinician rating of severity of psychopathology and treatment response. The CGI-I will be completed at time 2 and youth receiving a score of 1 ("very much improved") or 2 ("much improved") will be considered treatment responders. Finally, the child and parents will be asked to rate the recent severity of the child's anxiety symptoms on a 0 to 10 scale.

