C.9.e. Therapist Report Measures. The survey, conducted under IRB 14-002608, will be an adaptation of the measures used in a previous study¹⁵ and will inquire about demographic/practice information. Therapists will be asked to indicate whether or not they have used various interventions over the past 12 months with anxious children and adolescents (presented separately). Additionally, therapists will be asked about their beliefs about exposure. Therapists that provide study treatment will complete the exposure beliefs questionnaire again before and after treatment. The modified System Usability Scale plus AC items (mSUSplus; Bangor et al., 2008; Brooke, 2013). Therapists in all 3 trials will complete the mSUSplus. Therapist in Trial 1 will complete the SUS two weeks and six months after training. In Trials 2 and 3 therapists will complete the SUS as part of the post treatment measures.

C.9.f. Session Coding. All therapy sessions in the TAU and FTF-AC will be audio recorded and coded with a CBT for child anxiety Treatment Adherence scale that has been used in previous treatment studies,^{18,67,74} in addition to recording the amount of time spent planning and conducting exposure. Audio recording will be used rather than video, as it will be easier to set-up and transport if exposures are completed outside of the office. Electronic communication between therapists and patients will be automatically recorded and phone conversations will be summarized in writing. These contacts will also be coded for recommendations regarding exposure. 10% of sessions will be coded by two evaluators independently to examine inter-rater reliability.

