C.10.b.2. Aim 2: Assess feasibility, safety, acceptance, and impact of *Anxiety Coach*. Analyses for Trial 1 will consist of examining changes in therapist questionnaires via repeated measures analyses of variation and descriptively summarizing data on therapist use and ratings of acceptability. Most appropriately for the present design of Trials 2 and 3, descriptive statistics will be calculated on all fidelity (e.g., frequency of exposure), feasibility (e.g., quantity and content of communication between the therapist and project director, frequency of assessing the application), and clinical variables (e.g., means, standard deviations, percentage of patients continuing to meet diagnostic criteria). Consistent with the ultimate goal of generating estimates of the effect of *Anxiety Coach*, symptom change within Trials 2 and 3 will be compared between groups using repeated measures analysis of variance (RMANOVA) and the frequency of the therapists' use of exposure will be compared between the TAU and FTF-AC condition using analysis of covariance (ANCOVA) to control for diagnosis and symptom severity. Given that this project aims to test the feasibility of a fully powered RCT, analyses testing group differences will be considered exploratory. Although the use of RMANOVA and ANCOVA has significant limitations (i.e., the treatment of missing data), the small sample size and inclusion of multiple therapists does not permit the use of a more powerful statistical approach such as a mixed-effects regression model. However, exploratory analyses using mixed-effects regression model will be conducted. These analyses will be completed to assist in planning design and analysis of a fully powered RCT, rather than to provide interpretable results.

C.10.b.3. Aim 3: Develop a protocol for implementing *Anxiety Coach*. To develop a protocol for using *Anxiety Coach* to increase therapist fidelity to evidence-based CBT and provide treatment with minimal direct contact, the frequency and timing of contact between the project director and therapists as well as the therapist and patient will be used to construct guidelines for monitoring and interacting with therapists and patients. The questions from patients and therapists will be summarized qualitatively and used to refine *Anxiety Coach* and develop the educational component of the protocol.

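### Trial 1's practice items look back 12 months but are repeated two weeks and six months after training, so the two-week practice comparison is nearly uninformative and the six-month one is biased toward no change

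*Protocol*

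**What the plan says.** Protocol C.9.e (Therapist Report Measures) describes the practice part of the survey: "Therapists will be asked to indicate whether or not they have used various interventions over the past 12 months".

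C.7.g (Assessment Timeline) sets three administrations in Trial 1:
- Baseline: "Therapists in Trial 1 will complete the survey materials from Phase I inquiring about treatment practices and beliefs prior to receiving training".
- Two weeks after training: "the therapists will be asked to complete the same survey material plus measures assessing software usability".
- Six months: "6 months after the initial training, therapist will be asked to complete the survey material, usability measure, and a questionnaire about their actual use of" the app.

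The opening of C.9 words the last time point differently: "In Trial 1 therapists will complete study measures before training, two weeks after training, and then six months later". This could mean six months after the two-week survey.

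C.3.b (Trial 1) confirms that the repeated forms cover practice as well as attitudes: "questionnaires about how they treat child anxiety and their beliefs about treatment related issues". C.10.b.2 then states: "Analyses for Trial 1 will consist of examining changes in therapist questionnaires via repeated measures analyses of variation".

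Neither document shortens or re-anchors the look-back at the repeat administrations. Section 4.1.1.b describes the survey as collecting how often strategies are used and gives no window. The SAP does not mention the Trial 1 survey.

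**The concern.** A change analysis needs each follow-up answer to describe the period since the intervention. Here the recall window is longer than both follow-up intervals, so each follow-up answer mixes practice before and after training. The yes/no format adds a ceiling: once a therapist has truthfully answered yes at baseline, more use afterwards cannot register, and stopping registers only when the whole window is free of use.

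Aim 2 includes impact on behavior, and C.1 says all three trials examine whether the app can increase the frequency of exposure. In Trial 1 this survey is the only described measure of practice taken both before and after training. A flat result could reflect the instrument and not the app, and it would be a poor guide when choosing measures for the planned larger trial.

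**Working it through.** The plan gives no figure to reproduce here. The check is the overlap of the windows, followed by an illustration under stated assumptions.

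**Inputs.** Look-back of 12 months, yes/no (C.9.e). Follow-up at 2 weeks and 6 months after training (C.7.g), or about 6 months plus 2 weeks on the other reading of C.9.

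**Step 1: share of the look-back before training** = 1 − (time since training ÷ 12 months).
- Two weeks: 1 − 14/365.25 = 96.2%.
- Six months: 1 − 6/12 = 50.0%.
- Six months after the two-week survey: 1 − (0.5 + 14/365.25) = 46.2%.

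**Step 2: if the items record frequency over 12 months** (one reading of 4.1.1.b) and recall is even across the year, the observed change is the true change times the post-training share. A doubling (+100%) appears as about +4% at two weeks and +50% at six months.

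**Step 3: the yes/no item as described in C.9.e.** Assume use follows a Poisson process at λ per year, doubling at training. These rates are assumptions and are not in the documents. With f the post-training share of the window, P(yes) = 1 − exp(−λ[(1 − f) + 2f]). Matched six-month windows give 1 − exp(−λ/2) before training and 1 − exp(−λ) after.

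| λ per year | Baseline, 12-month | Two weeks | Six months | Fully post-training year | Matched six-month windows |
|---|---|---|---|---|---|
| 0.5 | 39.3% | 40.5% | 52.8% | 63.2% | 22.1% to 39.3% |
| 2 | 86.5% | 87.5% | 95.0% | 98.2% | 63.2% to 86.5% |
| 3 | 95.0% | 95.6% | 98.9% | 99.8% | 77.7% to 95.0% |

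At two weeks a doubling moves the yes proportion by about 1 point or less in every row. At six months the planned item shows about 13, 9 and 4 points, where matched windows would show about 17, 23 and 17. The loss is modest when prior use is rare and large when it is common.

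**Step 4: stopping.** A technique used 12 times a year and abandoned at training still reads yes at six months with probability 1 − exp(−12 × 0.5) = 99.8%.

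**Step 5: therapists answering no at baseline.** They had no use in the year before training, so a yes at six months can come only from use after training. For them the 12-month item and a since-training item give the same answer.

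**Step 6: why an existing 12-month baseline cannot be paired with a six-month item.** At λ = 2 with a true doubling, the baseline reads 1 − exp(−2) = 86.5% and a six-month since-training item reads 1 − exp(−4 × 0.5) = 86.5%, so the doubling disappears. With no true change, the second figure is 1 − exp(−2 × 0.5) = 63.2%, a false fall of about 23 points.

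**The case against.** The strongest reply is about stakes. C.3.b calls Trial 1 an acceptability study in which "we will gather acceptability and usability data from up to 30 therapists". It has no control arm, and C.10.a describes the study's analysis as primarily descriptive. Exposure frequency is compared in Trial 2, by ANCOVA (C.10.b.2), with sessions recorded and coded (C.9.f). No decision rule depends on the Trial 1 survey. All of this stands and limits the weight of the point. It does not remove it, because C.10.b.2 does specify the change analysis, and a descriptive summary of the same answers carries the same overlap.

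The second reply is that the wording is uncertain. The 12-month window appears once, for an adapted survey run under a separate IRB number, and the form is not in the documents. This also stands. If the repeat form uses a shorter window, the protocol should say so.

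A reader might infer three stronger things that the documents do not support:
- *That every follow-up answer is contaminated.* Step 5 shows otherwise for therapists answering no at baseline. C.3.a.4 and C.7.a aim to recruit infrequent users of exposure, so this group may matter, although C.4.a does not require infrequent use.
- *That Trial 1 has no other evidence on exposure.* C.3.b and C.9.f.2 provide automatic app records, including details of completed exposures, free of the 12-month window. They have no baseline and miss exposure done without the app, so they cannot show change in practice.
- *That the existing baseline could be rescaled to a monthly rate.* A yes/no answer holds no rate, and Step 6 shows the harm of mixing windows.

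**Conclusion.** The point holds for the practice-use items in Trial 1 only. As written, the two-week practice comparison is nearly uninformative (96% of the window precedes training), and the six-month comparison is biased toward no change (50%, or 46% on the other reading of C.9). Prior users cannot show an increase on the yes/no item and are slow to show a decrease; first-time adoption is captured without dilution.

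The overlap shares rest only on C.9.e and C.7.g meaning what they say. The percentages in Steps 3, 4 and 6 also rest on assumed use rates and a Poisson pattern. Belief and usability scales, and the exposure comparison in Trial 2, are not affected. This is a worthwhile correction to an exploratory analysis and not a threat to the study's main conclusions.

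**What to change.** 1. In C.7.g and C.9.e, remove the practice items from the two-week form and keep beliefs and usability. In C.10.b.2, limit the Trial 1 practice-change analysis to baseline versus six months.
2. For therapists not yet at baseline, ask about use in the past 6 months at baseline and since Anxiety Coach training at six months, with a frequency response. The windows are then equal and do not overlap.
3. For therapists who already gave a 12-month yes/no baseline, do not rescale it or compare it with a six-month item. Keep the 12-month item at six months and add a since-training item reported descriptively. Report new adoption among baseline no answers, and state the overlap as a limitation for the rest. New adoption should not be credited to training by itself: at an unchanged 0.5 uses per year, 1 − exp(−0.25) = 22.1% of baseline no answers would turn to yes by six months.
4. Reconcile C.9.e (yes/no, 12 months) with 4.1.1.b (frequency, no window), and C.7.g with C.9 on where the six months start.

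The cost is form wording and a narrower analysis. The items will no longer match the Phase I survey word for word, and therapists with a 12-month baseline cannot be pooled with later ones for practice change. That group may be most of the sample, since C.4 says Trial 1 therapists have largely been recruited. The SAP is written in the past tense; if collection is complete, what remains is to drop the two-week practice comparison, report new adoption, and state the limitation.
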